**Table 3. Study Management and Committees.** 

Committee	Role	Members	Frequency
Trial Management Committee (TMC)	To monitor all aspects of the conduct and progress of the trial, ensure that the protocol is adhered to and take appropriate action to safeguard participants and the quality of the trial.	
 
Principal Investigator from each hub*
 
Trial Coordinators
 
Project Administrator
 
Data Manager
 
All Investigators
 
	Weekly**  Biweekly to
ū	progress of the trial, including site-specific safety protocols within and across sites	•	•
Trial Steering Committee (TSC)	To provide overall supervision of the trial and ensure that it is being conducted in accordance with the protocol and the relevant regulations. The TSC should approve the trial protocol and any protocol amendments and provide advice to the TMC on all aspects of the trial. Decisions about continuation or termination of the trial or substantial amendments to the protocol are finally the responsibility of the TSC.	
 
Members of the TMC
 
All Investigators
 
Trial/Content Advisors and Consultants
 
	Six-monthly
Data Safety Monitoring Board (DSMB)	The DSMB will review the accruing trial serious adverse event reports to assess whether there are any safety issues that should be brought to participants' attention or any reasons for the trial not to continue. It is the only body that makes recommendations to unblind data and makes further recommendations to the TMC.	
 
[name] - clinical psychologist, with experience in BA
 
[name] - developmental pediatrician
 
[name] - psychologist experience on maternal depression
 
[name] - biostatistician with experience on mental health trials
 
	Six-monthly

\*hub refers to locality (Toronto, Chapel Hill, Chicago) \*\* weekly meetings also held within sites

Table 4. Protocol Summary Table.

Title	Scaling Up Maternal Mental healthcare by Increasing access to Treatment (SUMMIT)		
Sample Size	N = 1230		
Study Population	Women pregnant up to 36 weeks or 4-30 weeks postpartum, with an EPDS score ≥10 and capable of giving informed consent.		
Accrual Period	39 months; Recruitment starts January 2020 and ends Mar 31 2023		
Study Design	A multi-center randomized non-inferiority trial to test the choice of delivery mode and provider, implementing a brief evidence-based PT of BA for perinatal depressive and anxiety symptoms.		

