#### 2.2. Treatment and Intervention Arms

- **2.2.1. Treatment.** The intervention will consist of six to eight weekly sessions of BA delivered to each participant individually. The current manual (*Appendices B1 and B2 Treatment Manual and The PREMIUM Counselling for Relationships Manual, respectively*)) have been adapted from two well-established and tested manuals— the Alma Program for perinatal populations in Colorado and the Healthy Activity Program (HAP) from Goa, India, respectively. BA posits that the key to feeling less depressed is to increase enjoyable or fulfilling activities that align with one's values and targeting the mechanisms of patient activation. Unlike other cognitive behavioral interventions for depression, BA explicitly targets avoidant coping, treating it much like any other anxiety disorder. This should facilitate our secondary focus on anxiety. Key strategies include: psychoeducation, behavioral assessment, activity monitoring and structuring, activation of social networks, interpersonal effectiveness, and problem solving.
- **2.2.2. Treatment indicators. Compliance** is defined as attending a minimum of six sessions (reduced if patient has two consistent sessions of EPDS session-wise scores<10) over a period of four months unless a pregnancy- or COVID-related hiatus is experienced. Reasons for dropout will be recorded in the individual patient's treatment log (see SUMMIT Treatment Log Record Form, Appendix C Study Measures, pg 40) using a data capture and storage system called the Research Electronic Data Capture (REDCapTM). **Response** and **remission** will be defined as PHQ-9 of less than 10 and less than 5, respectively, at 3-months post-randomization. This period will be extended in the event that there is a hiatus to treatment due to significant perinatal-related life events (e.g., giving birth, obstetrical complications, COVID-19). Another indicator will include the estimation of comorbidity on both the EPDS and GAD-7.
- **2.2.3. Intervention Arms.** During regular operations participants will be randomized to one of four arms (Figure 2):

[figure not shown]

[figure not shown]
Figure 2. Intervention Arms

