Women will be contacted either by a trained research assistant, a treating physician or another member of the circle of care to ask whether they can be contacted by one of the trained research assistants. They will then receive a brief overview of the study by a research assistant, while an in-patient, visiting an out-patient clinic, or over the phone. Women who agree will then be fully informed of the study procedures by the research assistant, and given an informed consent form (see Informed Consent Form, Appendix E − Study Documents, pg 4 and 16) to review. Women will be given as much time as they need to decide whether they wish to participate, and the research assistant will answer all questions they may have. Once they sign the consent form, women will be screened using the Edinburgh Postnatal Scale for Depression (EPDS≥10^41) and General Anxiety Disorder (GAD)-7 for eligibility. If an EPDS administered in the last 7 days is in the patient's clinical chart, we will use and enter that score for screening instead of asking the patient to complete the scale again. In the interest of patient-centered care, women who give their permission may also complete informed consent

over the phone, witnessed by a third-party. These women will be mailed a consent form and be fully informed of the study procedures by the research assistant over the phone. If they decide that they want to participate, they will give verbal consent verified by a third-party (a second study team member), and will then be emailed links to screening measures. These women will be provided with a self-addressed, stamped envelope to mail their signed consent forms back to the site, and will then be sent a consent form with their own signature and the name and signature of the RA who obtained their informed consent for their files.

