Depressive Symptoms ⁸	Edinburgh Postnatal Depression Scale (EPDS) ^{8,9}	Mean continuous score of a 10-item scale (0-30). Severity ranges: none or minimal depression (0-9), mild (10-11), moderate (12-19), severe (>19)
Anxiety Symptoms	Generalized Anxiety Disorder Scale (GAD-7) ^{10,11}	Mean continuous score of a 7-item scale (0-21). Cut-off value (10)
Response & Remission	Patient Health Questionnaire-9 (PHQ-9) ¹²	Response: PHQ<10 Remission is defined as PHQ<5
Perceived Support	Multidimensional Scale of Perceived Social Support (MSPSS) ¹³	Mean continuous score of a 12-item scale (1-84)
Disability Assessment	World Health Organization Disability Assessment Schedule (WHODAS) ¹⁴	Mean continuous score of a 12-item scale (0 – 48)
Quality of Life Assessment	EQ5D-5 Level (EQ5D-5L) ¹⁵	Mean continuous score of a 5-item scale (1-25)
Trauma Symptoms	Abbreviated PTSD Checklist (PCL-6) ¹⁶⁻¹⁸	Mean continuous score of a 6-item scale (1-30). Cut-off value [14 (threshold) and 8 (subthreshold)]
Patient-Reported Activation	Premium Abbreviated Activation Scale ^{19, 20}	Mean continuous score of a 5-item scale (0-20)
Patient Satisfaction***	Client Satisfaction Questionnaire-8 (CSQ-8) ²¹	Mean continuous score of an 8-item scale (1-32)
Therapeutic Alliance***	Working Alliance Inventory-Short Revise (WAI-SR) ²²	Mean continuous score of a 12-item scale (1-60)
Health Service Utilization	Health Service Utilization Questionnaire (HSU-Q) ²³	Total score of a 16-item scale (0-32)
Treatment Preference**	Delivery of treatment and treatment provider preference	Score of 0 or 1
COVID-19 Exposure ⁹	1-item question on COVID-19 exposure	Self-reported
Health Benefits Access and Use	2-item question on access and use of health benefits	Self-reported
Treatment: Measured at every session during treatment, unless otherwise indicated		
Dosage	Treatment Log ²⁴	Number of Sessions Attended
Therapy Quality****	Quality of Healthy Activity Program (Q-HAP) ²⁵	Mean continuous score of treatment-specific BA skills (0-4) and general counselling skills (0-4)
Session Depressive / Anxiety	Session-by-session EPDS ⁸ and GAD-7 ¹⁰ scores	Mean continuous score of a 10-item scale (0-30) on EPDS and of a 7-item scale (0-21) on GAD-7
Homework Adherence	Treatment Log ²⁴	Mean continuous score of a 1-item question (0-2)
Adverse or Serious AEs	Anytime an Adverse Event (AE) or Serious AE (SAE) occurs	Any event that represents a serious threat to the safety of the mother or her child (see Appendix D of protocol)

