1.6.1. Primary Aim 1 (Specialist vs. Non-Specialist) Comparison

The primary outcome measure is an EPDS mean score at 3 months post-randomization. The sample size calculation is based on an EPDS mean estimate of 7.93 (SD=4.68)³⁰. Using a non-inferiority margin of 10% (i.e., EPDS score of 0.79 in relation to the mean), and an alpha=0.05, we require 431 participants in each of the two groups (SP, NSP) to provide greater than 80% power ([Table 3](#)). To account for 10% drop out, the sample size is inflated to **N=958** (479 per group, SP vs. NSP). All sample size calculations were run using PASS Version 12³¹.

Table 3: Power Analysis of a Non-Inferiority Test of the Difference of Two Means

Power	N1/N2	Non-Inferiority Margin (NIM)	Actual Difference	Significance Level (Alpha)	Beta	Standard Deviation 1 (SD1)	Standard Deviation 2 (SD2)
0.80022	431/431	0.793	0.000	0.05000	0.19978	4.680	4.680

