Appendix 1. List of Variables

VARIABLE	MEASURE	TIME OF ASSESSMENT						
		SCREENING	BASELINE	SESSION-WISE	3 MONTHS	6 MONTHS	12 MONTHS	HOME VISIT
PRIMARY OUTCOME								
Depressive symptoms	Edinburgh Postnatal Depression Scale (EPDS)							
SECONDARY OUTCOMES								
Depressive symptoms	Edinburgh Postnatal Depression Scale (EPDS)							
Anxiety Symptoms	General Anxiety Disorder-7 (GAD-7)							
Child Mental Development	Bayley-IV							
Psychosocial Stimulation	Home Observation Measurement Evaluation (HOME)							
EXPLORATORY OUTCOMES								
Response & Remission	Patient Health Questionnaire (PHQ-9)							
Suicide Risk*	Columbia Suicide Severity Risk Screener (C-SSRS)							
Patient-Reported Activation	Premium Abbreviated Activation Scale (PAAS)							
Quality of Life Assessment	EQ5D-5-level (EQ5D-5L)							

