Appendix 2. Cut-off Values, Severity Classification and Psychometric Properties for Key Outcomes

Outcome	Instrument	Values	Cronbach's Alpha**
Depressive Symptoms	Edinburgh Postnatal Depression Scale (EPDS)	-Cut-off: EPDS total score $\geq 10^{8, 67}$ -Severity Classification ^{9*} : 
• 0-9: None• 10-11: Mild• 12-19: Moderate• 20-30: Severe	0.86
Anxiety Symptoms	Generalized Anxiety Disorder Scale (GAD-7)	-Cut-off: GAD-7 total score $\geq 10^{11}$ -Severity Classification ¹⁰ : 
• 0-4: None• 5-9: Mild• 10-14: Moderate• 15-21: Severe	0.90
Response & Remission	Patient Health Questionnaire-9 (PHQ-9)	-Cut-offs ⁶⁸ : 
• Response: PHQ-9 total score < 10• Remission: PHQ-9 total score < 5 -Severity Classification ⁶⁹ : 
• 0-4: None• 5-9: Mild• 10-14: Moderate• 15+: Moderately severe & severe	0.87
Trauma Symptoms	Abbreviated PTSD Checklist (PCL-6)	-Cut-off: PCL-6 total score $14^{16, 18, 70}$ -Severity Classification ¹⁸ : 
• 6-12: Low risk• 13-16: Medium risk• 17-25: High risk• 26-30: Very high risk	0.86
Disability Assessment	World Health Organization Disability Assessment Schedule (WHODAS)	-Cut-off: WHODAS total score $3.1^{14, 71}$	0.91
Child Mental Development	Bayley Child Mental Development Scales IV	-Mean score: 100	
• Cognitive: 0.90• Receptive Language: 0.93• Expressive Language: 0.90
Perceived Support	Multidimensional Scale of Perceived Social Support (MSPSS)	Not Applicable	0.95
Patient-Reported Activation	Premium Abbreviated Activation Scale (PAAS)	Not Applicable	0.81
Therapy Quality	Q-SUMMIT	Not applicable	
• Treatment-specific Skills: 0.86• General Skills: 0.94

*In addition to previously-established cut-offs, an exploratory analysis using ROC curve will be conducted to compare symptom severity categories between the EPDS and PHQ-9.

**Cronbach's alpha for these measures were conducted between August 2022 and March 2023 and based on a minimum sample size of $n=279$.

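### Response and remission are 3-month PHQ-9 cut-offs with no baseline condition, so a woman who enters below a cut-off and is still below it counts as a success without having improved

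*Protocol*

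**What the plan says.** **Outcome.** Protocol 2.2.2 (Treatment indicators) states that response and remission "will be defined as PHQ-9 of less than 10 and less than 5, respectively, at 3-months post-randomization". Protocol Table 6 and SAP Table 2 repeat the pair ("Remission is defined as PHQ<5"), as does SAP Appendix 2 ("Response: PHQ-9 total score < 10"). None of the four places refers to the woman's own baseline PHQ-9, asks for a change from it, or restricts the denominator.

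**Entry.** Protocol Table 4 describes the population as women "with an EPDS score ≥10 and capable of giving informed consent" (the last words concern consent). Protocol Table 5 and SAP Table 1 set the same EPDS threshold and no PHQ-9 threshold. Protocol 2.7.1 says "women will be screened using the Edinburgh Postnatal Scale for Depression (EPDS≥10", together with the GAD-7; the PHQ-9 is not named there. SAP Table 2 and Appendix 2 class EPDS 10-11 as mild, so mildly symptomatic women are eligible.

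**Timing and rank.** In SAP Appendix 1 the row for "Patient Health Questionnaire (PHQ-9" is ticked at baseline and at 3, 6 and 12 months, not at screening. It stands under exploratory outcomes.

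**The concern.** Response and remission are normally read as something that happened after treatment began. Here they are states at follow-up, measured on a different scale from the one used for entry. A woman with EPDS 11 and PHQ-9 8 at entry already meets the response cut-off before her first session. If her PHQ-9 is 8 or 9 at 3 months she is reported as a responder. A woman with PHQ-9 4 at entry already meets both cut-offs.

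Two things are at stake for this outcome. First, the rate called response may be higher than the rate among women who had something to respond from. Second, women who start below the cut-off and stay there add a similar number of successes to each arm, which can make the arms look more alike than they are among the other women.

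**Working it through.** **1. Is there a figure to reproduce?** No. Neither document gives an expected rate, margin, power or sample size for response or remission. The stated margins belong to other outcomes; for the provider comparison on the primary EPDS score, SAP 1.6.1 reads "Using a non-inferiority margin of 10% (i.e., EPDS score of 0.79 in relation to the mean), and an alpha=0.05".

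**2. Can a woman enter below the cut-off?** The documents allow it.
- Eligibility sets no PHQ-9 minimum.
- SAP 1.6.2.1 calls the two scales comparable, but neither document shows that EPDS ≥10 implies PHQ-9 ≥10. SAP Appendix 2 leaves the mapping open: "an exploratory analysis using ROC curve will be conducted to compare symptom severity categories between the EPDS and PHQ-9".
- Protocol 2.7.1 accepts a chart EPDS up to 7 days old for screening, while the PHQ-9 is taken at baseline. The two scores need not be from the same day.
- In SAP Appendix 2, PHQ-9 0-4 is none and 5-9 is mild. A woman in either band at baseline already satisfies the response cut-off.

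**3. Is baseline PHQ-9 used for these outcomes?** It is collected, and SAP 3.4.1 plans descriptive statistics and baseline comparisons by group. But no analysis section (Protocol 3.5.1 to 3.5.3, SAP 3.4.1 to 3.4.2.5) uses it to define or analyse response or remission.

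**4. Effect on the rate.** Let x be the share below the cut-off at entry, s the share of those women still below at 3 months, and r the response rate among women at or above the cut-off at entry.

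Reported rate = x·s + (1 − x)·r

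Reported rate − r = x·(s − r), so the rate is inflated relative to r only if s > r.

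**5. Effect on the difference between arms 1 and 2.**

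Reported difference = x·(s1 − s2) + (1 − x)·(r1 − r2)

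If s1 = s2, this is (1 − x)·(r1 − r2), whatever the common value of s.

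**6. Illustration.** All inputs are assumptions: r = 60% and 50%, s = 90% in both arms, x from 10% to 50%.

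| x | Arm 1 | Arm 2 | Difference | Rate if r = 0 (x·s) |
|---|---|---|---|---|
| 10% | 63% | 54% | 9 points | 9% |
| 20% | 66% | 58% | 8 points | 18% |
| 30% | 69% | 62% | 7 points | 27% |
| 40% | 72% | 66% | 6 points | 36% |
| 50% | 75% | 70% | 5 points | 45% |

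Worked row, x = 20%: 0.2 × 0.9 + 0.8 × 0.6 = 0.66, and 0.2 × 0.9 + 0.8 × 0.5 = 0.58.

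With s = 80% or 100% in both arms, the rates at x = 30% are 66% against 59%, or 72% against 65%; the difference is 7 points each time.

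**7. When the dilution fails.** With x = 30%, s = 90% against 80% and the same r, the rates are 0.27 + 0.42 = 69% and 0.24 + 0.35 = 59%. The difference is again 10 points. The shrinkage by (1 − x) therefore depends on a similar s across arms.

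**8. Remission.** The same formulas apply with x as the share below 5 at entry. Anyone below 5 is below 10, so this x cannot exceed the one for response.

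**The case against.** **The trial's conclusions do not rest on this outcome.** This stands. A reader might infer that, in a non-inferiority trial, dilution here helps the hoped-for result. The documents do not support that reading. Both primary tests use the continuous 3-month EPDS score (SAP 3.4.1), and the secondary ones use the GAD-7 (SAP 3.4.2.1). Response and remission have no margin and no named between-arm test. The rank is slightly blurred, because SAP 1.4 says Table 2 lists primary and secondary outcomes and the pair appears there. But Table 2 assigns no ranks, and Appendix 1 says exploratory.

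**Not every woman below the cut-off at entry is a success.** This also stands. All participants have screened at EPDS ≥10 and can worsen; one whose PHQ-9 reaches 10 or more at 3 months is not a responder. Whether provider or mode affects such worsening is a fair part of a whole-sample comparison.

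**The size is hypothetical.** Correct. Nothing in the documents fixes x, s or r, so no particular amount of inflation or dilution is demonstrated.

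**The cut-offs are referenced, consistent across both documents, and a whole-sample end-state rate is a coherent quantity.** Agreed, and this argues for keeping that rate. It does not justify the name. The source cited in SAP Appendix 2 concerns, by its title, severe depression, whereas this trial admits women from the mild EPDS band. An end state that includes women who never had to change is not response.

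**Replacing the definition would bring its own problems.** With baseline minima of 10 for response and 5 for remission, a woman entering at 5-9 could remit but could not be assessed for response. The protocol (V20, 25 October 2024) also post-dates the stated study end of 31 May 2024, so a replacement would be a late redefinition. For both reasons the fix adds to the definition and renames it, and does not replace it.

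**Conclusion.** The point holds for response and remission as labelled outcomes. As written, the rule counts a woman who goes from PHQ-9 8 to 9 as a responder. This follows from the stated cut-offs and entry criteria and needs no assumption.

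The numerical effect is conditional. The response rate is inflated if women who start below the cut-off stay below it more often than others cross it. A between-arm risk difference shrinks by (1 − x) if the stay-below rate is similar across arms. For x of 10% to 50%, an assumed 10-point difference becomes 9 to 5 points. The share x is not given, so the actual size is unknown until the baseline counts are tabulated.

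The primary EPDS and secondary GAD-7 non-inferiority conclusions are unaffected. The matter is worth correcting because response and remission rates are easily quoted whatever their rank, and because the data needed are already collected.

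**What to change.** In Protocol 2.2.2 and Table 6, and in SAP Table 2 and Appendix 2:

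1. Keep the whole-sample rate, but label it *PHQ-9 below 10* and *PHQ-9 below 5 at 3 months*, not response and remission.
2. Report by arm the number and percentage of women below each cut-off at baseline.
3. Report response among women with baseline PHQ-9 ≥10, and remission among women with a stated baseline minimum. That minimum can be ≥5, or ≥10 so that both outcomes share one denominator; the SAP should say which. The restriction uses a variable measured before randomization, so it keeps the randomized comparison within the subset.
4. Date the change. If outcome data by arm have already been examined, label the restricted rates as post hoc.

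**Cost.** Wording and a few extra table rows. No new data are needed, and the primary analysis and its sample size do not change. The price is a smaller denominator for the restricted rates and probably a less favourable headline figure.

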#### 2.3 Non-Specialists: Recruitment, Training, Supervision and Selection

- **2.3.1 Recruitment.** Recruitment of NSPs will be based on the aforementioned inclusion/exclusion criteria as well an expressed desire to help women with depressive and anxiety symptoms. During recruitment, a selection interview will take place, whereby NSPs are assessed based on their common skills—the style with which they interact with a mock patient—using the Therapy Quality Scale. We have used this method previously and found that it correlates with trainee competency. Trainee providers will be recruited by placing advertisements in newspapers and through word of mouth, and selected based on their performance in a structured interview and role-play during an intake interview. The same procedures will be implemented in each hub.
- **2.3.2.** Training & Competency Tests. In Fall 2019, those trainees selected will be invited to participate in a 5-day participatory training workshop covering the manualized BA treatment for perinatal mental health populations (*Appendix B1 Treatment Manual*) and an adapted version of The PREMIUM Counselling for Relationships Manual (*Appendix B2 The PREMIUM Counselling for Relationships Manual*). Trainees who meet competency standards (based on a multiple-choice questionnaire used for another BA trial; *see Competency Measure Survey, Appendix C Study Measures*, pg 49) and in an interaction with a standardized patient (actor) rated by experts using an adapted version of the Q-HAP (*see Quality of Healthy Activity Program (Q-HAP), Appendix C Study Measures*, pg 45) will be selected for the 8-week internship phase of the trial. During the internship phase, trainees will see up to 2 participants (one via telemedicine and one in-person) to implement the BA treatment. In addition, all trainees will receive training in the safety protocols (*see Appendix A*).
- **2.3.3. Supervision.** The trainees will receive weekly group supervision from the hub intervention lead (see Table 1 above). All intervention leads are co-l's on the current study, with a minimum of 10 years' experience training and supervising lay and specialist therapists in psychological treatments and who have allocated time to focus on providing training and

supervision to NSPs. Therapy quality will be assessed using a reliable and validated tool (an adapted version of the Q-HAP; see Quality of Healthy Activity Program (Q-HAP), Appendix C – Study Measures, pg 45). As the trainee counsellors gain experience in delivering the intervention, the supervision format will evolve from expert led (that is, the clinical lead and specialist who is skilled in the delivery of the PT) to peer-led group supervision. All treatment providers will record all BA sessions for training and supervision purposes and for fidelity measures.

- **2.3.4. Selection.** Only trainees who achieve competence, as assessed by standardised role-plays and therapy quality assessments, will be selected to deliver BA during the trial.
- **2.4 Specialists.** Specialists will include a wide range of specialties (e.g., psychiatrists, clinical and counseling psychologists, social workers) with a minimum of 5 years of formal experience in delivering psychological treatments. They will be recruited through word-of-mouth and based on their location, interest and availability, and good standing with their respective colleges. In Fall 2019, specialists will also receive the BA workshop followed by an internship phase where they will see up to 2 participants each with expert-led supervision followed by guided peersupervision. The primary focus of the workshop for the specialists will be on the contents of the BA manual.

To assess provider proficiency with telemedicine, we will collect information from the trainees about their perceived telemedicine proficiency at the end of training and then after their last session with each participant during the internship phase (see SUMMIT Perceived Telemedicine Platform Proficiency Self-Assessment Questionnaire (for providers), Appendix C – Study Measures, pg 105). Participants assigned to the given provider will also be asked to rate their provider's telemedicine proficiency after their last session (see SUMMIT Perceived Telemedicine Platform Proficiency Self-Assessment Questionnaire (for participants), Appendix C – Study Measures, pg 105). The questionnaire is a brief, 5-item scale rated from 0 (Strongly Disagree) to 4 (Strongly Agree).

